8.3 Analysis of Study Endpoints

8.3.1 Analysis of Primary Endpoints for Efficacy

The following are the primary efficacy endpoints for both phases;

1. Overall Tumor Response (measured by RECIST 1.1);
2. Progression-Free Survival (PFS)

These endpoints are well established and commonly used to evaluate signs of clinical activity and efficacy.

The overall tumor response rates will be tabulated for all patients by treatment stage. PFS is defined as the time from treatment start until disease progression or death whichever occurred earlier. Patients who have not progressed or who are still alive at the time of evaluation will be censored for the analysis.

KM method will be used for estimating median times for PFS. The 95% confidence intervals of the medians will be presented.

Subject disposition, demographic and baseline subject characteristics will be summarized separately for Stage 1 and Stage 2. AEs will be classified and summarized by type, incidence, severity, and causality. All AEs will be summarized by subject, treatment, and disease. All subjects who receive at least 1 dose of ADXS11-001 will be included in the safety analyses.

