2 TRIAL DESIGN

Specific procedures to be performed during this trial, as well as the prescribed times and associated visit windows are outlined in the Schedule of Events- [Section 6.1](#). Details of each procedure are provided in [Section 7.1](#) - Trial Procedures.

This is a multi-center, open-label, 2 stage monotherapy study of ADXS11-001 in subjects with persistent/recurrent, loco-regional or metastatic SCCA of the anorectal canal that was previously treated in the metastatic setting. Stage 1 of the study will evaluate the safety and efficacy of ADXS11-001. After 31 evaluable subjects have been enrolled, further accrual will be temporarily stopped in Stage 1 to complete an interim efficacy

analysis evaluation. If the efficacy from Stage 1 demonstrates a response rate $\geq 10\%$ by either RECIST 1.1 or 6-month progression free survival (PFS) rate $\geq 20\%$, enrollment will re-open to Stage 2. Enrollment will be complete in Stage 2 when an additional 24 evaluable subjects have been accrued (total 55).

Subjects will be treated with intravenous (IV) ADXS11-001 administered over [REDACTED] every 3 weeks at a dose of 5×10^9 CFU for up to 2 years or until a discontinuation criterion is met. A treatment cycle is defined as 9 weeks. Tumor assessments will occur every 9 weeks (Week 8 of every Cycle). Subjects will be monitored for adverse events (AEs) throughout the study; AEs will be graded in severity according to the guidelines outlined in the NCI Common Toxicity Terminology Criteria for Adverse Events (CTCAE) version 4.0.

Safety follow-up will be conducted via telephone call 30 days (± 5 days) after the last ADXS11-001 infusion to confirm the resolution of any ongoing AEs and SAEs. Survival Follow-Up will be conducted at each visit during the Lm Surveillance period and via a telephone call every 3 months (± 2 weeks) after the Lm Surveillance period to determine survival status for all subjects.

The end of the study will be defined as 1 year after the last subject has enrolled on study. However, any ongoing subjects, subjects who are still deriving clinical benefit from ADXS11-001 therapy at the end of their 2-year treatment period or at the end of the study may be enrolled into a separate extension study, as available.

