8.2 Sample Size and the Design

This is a multi-center, open-label, 2 stage monotherapy study of ADXS11-001 in subjects with persistent/recurrent, loco-regional or metastatic SCCA of the anorectal canal that was previously treated in the metastatic setting.

Primary Efficacy Measures are:

1. The overall response
2. Progression-Free Survival (PFS)

We employed a 2-stage design for testing these 2 primary efficacy measures. Simon's 2-stage method is not directly applicable because it is for single proportion type endpoint. However, we used Simon's method with null and alternative response rates of 10% in Stage 1 and 20% in Stage 2 to obtain the total sample sizes for both stages and use the Multinomial Two-Stage approach proposed by Benny Zee, *et al* (1999) [24] to obtain the stopping probabilities.

By Simon's method, we need to enroll 31 subjects at Stage 1 and an additional 24 subjects in Stage 2 if 3 or more responses are observed in Stage 1. Based on this sample size plan, we formed the following 2 endpoints, 2-stage framework:

In Stage 1 of the study, we will enroll 31 subjects. The safety and efficacy data of the subjects will be evaluated. After 31 evaluable subjects have been enrolled, further accrual will be temporarily stopped in Stage 1 for an efficacy interim analysis evaluation. If the efficacy from Stage 1 demonstrates a response rate $\geq 10\%$ or 6-month PFS $\geq 20\%$,

the enrollment will re-open to Stage 2. The enrollment will be complete in Stage 2 when an additional 24 evaluable have been accrued (total from Stages 1 and 2 = 55).

The hypothesis testing in Stage 1 is given in the following:

- Stage 1:
 - Null Hypothesis (H_0): Response rates (r_1) <10% and 6-month PFS rate (p_1) <20%;
 - Alternative Hypothesis (H_a): Response rates (r_1) \geq 10% or 6-month PFS rate (p_1) \geq 20%
- Stage 2:
 - Null Hypothesis (H_0): Response rates (r_2) \leq 25% and 6-month PFS rate (p_2) \leq 50%;
 - Alternative Hypothesis (H_a): Response rates (r_2) \geq 25% or 6-month PFS rate (p_2) \geq 50%

Using the Multinomial Two-Stage approach proposed by Benny Zee, *et al* (1999),[\[24\]](#) we simulated 50,000 trials to examine the Type I and II errors under this design assumption. The following estimates, including Type I and II errors, from these simulations are summarized in the following table.

Type I	Type II
Type I Error = 0.03236 ASN for H0 = 32.20192 P(stop early H0) = 0.94992	Power = 0.924

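### The PFS censoring sentence in section 8.3.1 contradicts the PFS definition just before it; programmed literally, it would bias PFS upward

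*Combined protocol and SAP*

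**What the plan says.** Section 8.3.1 gives two adjacent statements about PFS, one of the two primary efficacy measures.

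- The event: "PFS is defined as the time from treatment start until disease progression or death whichever occurred earlier".
- The censoring: "Patients who have not progressed or who are still alive at the time of evaluation will be censored for the analysis".

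For estimation it adds that "KM method will be used for estimating median times for PFS", with 95% confidence intervals for the medians. It does not say on what date a censored subject is censored, or which sentence governs if they disagree. Section 8.1 defers analysis details to a Statistical Analysis Plan; the text reviewed contains no other PFS censoring rule.

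PFS also feeds a decision. Sections 2 and 8.2 reopen enrollment for Stage 2 if the Stage 1 response rate is at least 10% or 6-month PFS is at least 20%. The Stage 1 null hypothesis is "Response rates (r_1) <10% and 6-month PFS rate (p_1) <20"%, and the Stage 2 PFS threshold is 50%. Stage 1 has 31 subjects and the total is 55.

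**The concern.** A PFS analysis should censor a subject only when neither event has happened, that is, when the subject is alive *and* has not progressed. The sentence joins the two conditions with *or*, so meeting either one is enough. Every living subject then qualifies, including one with documented progression. So does every subject who died before progressing.

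The first of these groups is an ordinary one in this trial. Section 5.10 lets subjects continue treatment after initial radiologic progression, exclusion criterion 19 removes those with life expectancy under 6 months, and survival is followed through the *Lm* surveillance period and beyond. Many subjects could therefore be alive after progression when the data are cut.

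At stake is a primary endpoint that can open Stage 2 without a qualifying response rate. The trial is single-arm, so no control group would make an inflated PFS visible.

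**Working it through.** No figure in the plan rests on the censoring rule, so there is none to reproduce. The check is one of logic, then direction, then size.

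**1. The two sentences across the four possible states**

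| State at evaluation | Under the definition | Under the censoring sentence, read literally |
|---|---|---|
| Alive, not progressed | Censored | Censored |
| Progressed, alive | Event | Censored (still alive) |
| Died without progression | Event | Censored (not progressed) |
| Progressed, then died | Event | Event |

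Two of the three event states are lost.

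**2. Direction**

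The Kaplan-Meier estimate is S(t) = ∏(1 − dᵢ/nᵢ) over event times up to t. Recoding an event as censored on the same date removes a factor below 1 and leaves the other risk sets unchanged, so S(t) can only rise. Moving that censoring to a later date enlarges later risk sets, so S(t) can only rise further. On the same data the literal rule never gives a lower estimate than the definition.

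**3. Size at a final cut (simulation, 1,500 trials per scenario)**

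From the documents: n = 31 + 24 = 55, and a data cut 12 months after last enrollment, since "The end of the study will be defined as 1 year after the last subject has enrolled on study". Assumed, not in the documents: uniform accrual over 24 months; exponential PFS; 90% of first events are progression; median post-progression survival of 3, 6, 12 or 24 months. A true 6-month PFS of 20% corresponds to a median of 6·ln 2/ln 5 = 2.58 months.

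Under the definition, the mean estimate recovers the truth (0.20 or 0.50). Under the literal rule:

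| Post-progression median (months) | 3 | 6 | 12 | 24 |
|---|---|---|---|---|
| Truth 20%: subjects counted as events (99% under the definition) | 86% | 77% | 60% | 38% |
| Truth 20%: 6-month PFS, censored at progression or death date | 24% | 28% | 37% | 53% |
| Truth 20%: same, progressed-and-alive censored at last follow-up | 25% | 32% | 47% | 66% |
| Truth 20%: median PFS in months, censored at progression or death date | 2.9 | 3.2 | 4.1 | 6.6 |
| Truth 50%: 6-month PFS, censored at progression or death date | 55% | 58% | 66% | 76% |
| Truth 50%: same, progressed-and-alive censored at last follow-up | 55% | 59% | 68% | 79% |

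With a true value of 20% and censoring at the progression or death date, the excess runs from 24 − 20 = 4 points to 53 − 20 = 33 points. If only 70% of first events are progression, the 6-month scenario moves from 28% to 37%.

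**4. Size at an early Stage 1 cut (3,000 trials per scenario)**

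The interim look comes when more progressed subjects are still alive, so more events are lost. Assumed: n = 31, 12-month uniform accrual, cut 6 months after last enrollment, other inputs as above, censoring at the progression or death date.

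- True 6-month PFS 20%: the literal estimate averages about 31% to 72% across the four scenarios.
- True 6-month PFS 10%, where the PFS criterion should fail: the definition gives a mean of 0.10 and about a 3% chance of an estimate of at least 20%. The literal rule gives means of about 0.18 / 0.28 / 0.45 / 0.63 and chances of about 41% / 76% / 95% / 99%.

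**The case against.** The strongest reply is that the definition is explicit and sits immediately before the faulty sentence. A competent analyst would not censor documented progression in a PFS analysis, would read the sentence as meaning alive and event-free, and would get no bias. That stands: the harm is conditional on literal programming. It does not remove the conflict, because the faulty sentence is the only instruction in the text on whom to censor.

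Second, section 8.3.1 ties Kaplan-Meier to median PFS, while the Stage 2 criterion is a 6-month rate within a multinomial two-stage design. The documents do not say how that rate is estimated. This also stands. A proportion counted directly from scans and deaths would be untouched; a Kaplan-Meier rate, or a proportion built from the same event flags, would inherit the error.

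Third, details are deferred to a SAP, which may put this right. That limits certainty about the consequence, but does not justify leaving the protocol sentence as it is.

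**Conclusion.** The wording conflict is certain. The censoring sentence is wrong for a primary endpoint, and if followed it biases PFS upward. The amount is not fixed by the documents: for a true 6-month PFS of 20%, about 24–53% at the final cut and about 31–72% at the early cut, given the accrual, event-mix and post-progression survival assumptions above. An estimate that high could wrongly meet the 20% criterion, provided the 6-month rate is a Kaplan-Meier estimate using this rule.

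A reader might infer more: that the literal rule turns PFS into overall survival, so that PFS must be grossly overstated and the 20% criterion is bound to be met. The documents do not support this. The rule changes who counts as an event, not when: a subject who progressed and then died still has the event at progression. For a true 6-month PFS of 20% and median survival of 8, 12 or 16 months (all first events taken as progression, the same 24-month accrual and 12-month follow-up), the literal estimate is 22/27/34% with censoring at progression, or 24/34/45% with censoring at cut-off, against 6-month survival of 64/78/85%. With 12-month accrual and 6 months of follow-up it rises to 31/43/53% or 39/56/67%, still below survival. The overstatement can be as small as 2 points (22 against 20).

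**What to change.** Replace the censoring sentence in section 8.3.1 with wording such as: *Patients who are alive and have not progressed at the data cut-off will be censored at their last evaluable tumor assessment; progression or death from any cause is an event.* Apply the rule to PFS by RECIST 1.1 and by irRECIST, and to the 6-month PFS rate used for the Stage 2 decision, stating how that rate is estimated. Carry the same text into the SAP before any PFS programming.

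The cost is one sentence in the protocol and SAP, plus a line on the 6-month estimator. No visit, scan or data field changes.

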8.4 Safety Monitoring

An external Data Safety Monitoring Committee will not be established for this study. A periodic safety review will be applied by an internal safety review team with medical capabilities to review individual and summary data collected in the safety and clinical databases. Findings having immediate implication for the management of subjects on study will be communicated to all Investigators in the timeframe associated with unexpected and drug-related SAEs.

8.5 Analysis of Safety Data

All AEs will be summarized by patient, treatment, and prior recurrence history (aggressive [recurrence within 2 years]/non-aggressive).

The NCI CTCAE v 4.0 will be used for AE grading (Grades 1 to 4). AEs will be classified using the Medical Dictionary for Regulatory Activities (MedDRA®) coding system.

The overall incidence of AEs will be summarized and classified by body system and by treatment group. An AE will be summarized if the onset date occurs anytime during study treatment or up to 30 days after the last dose of study treatment; or, if it occurs prior to Day 1 and worsens while on therapy. The type, incidence, severity, and causality of each AE, the duration of the event, and any required treatment interventions will be tabulated.

Physical examination results will be presented in the patient data listings. Vital sign measurements will be summarized at each infusion using descriptive statistics. The incidence of clinically significant laboratory abnormalities will be presented, and laboratory data will be summarized at each infusion by the NCI CTCAE v 4.0 toxicity grades. Laboratory data will be presented for patients having Grade 3 or 4 changes from baseline.

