5 METHODOLOGY

5.1 Entry Criteria

5.1.1 Inclusion Criteria

This study will include subjects with persistent/recurrent, loco-regional or metastatic SCCA of the anorectal canal.

For subjects to be eligible they:

1. Must have histopathologic diagnosis of squamous cell cancer of the anorectal canal.
 2. Must have received at least one line of therapy for their metastatic disease. However patients deemed by their investigator as not optimal candidates for chemotherapy (e.g., drug allergy, ototoxicity, renal insufficiency) would be considered eligible.
 3. Be willing and able to provide written informed consent for the trial.
 4. Be ≥ 18 years of age on day of signing informed consent.
 5. Have measurable disease based on RECIST 1.1
 6. Have Eastern Cooperative Oncology Group (ECOG) performance status of 0 or 1.
 7. Demonstrate adequate organ function as defined in [Table 3](#).
-

Table 3 Adequate Organ Function Laboratory Values

System	Laboratory Value
Hematological	
Absolute neutrophil count (ANC) ^a	≥1,000 /mcL
Platelets	≥75,000 / mcL
Hemoglobin	≥9 g/dL or ≥5.6 mmol/L
Renal	
Serum creatinine OR Measured or calculated ^b creatinine clearance (GFR can also be used in place of creatinine or CrCl)	≤1.5 X upper limit of normal (ULN) OR ≥50 mL/min for subject with creatinine levels >1.5 X institutional ULN
Hepatic	
Serum total bilirubin	≤1.5 X ULN OR Direct bilirubin ≤ULN for subjects with total bilirubin levels >1.5 ULN
AST (SGOT) and ALT (SGPT)	≤2.5 X ULN OR ≤5.0 X ULN for subjects with liver metastases
Coagulation	
International Normalized Ratio (INR) or Prothrombin Time (PT)	≤1.5 X ULN unless subject is receiving anticoagulant therapy as long as PT or INR is within therapeutic range of intended use of anticoagulants
Activated Partial Thromboplastin Time (aPTT)	≤1.5 X ULN unless subject is receiving anticoagulant therapy as long as aPTT is within therapeutic range of intended use of anticoagulants
^a ANC, Platelets, Hemoglobin requirement cannot be met by the use of recent transfusions, or growth factor support (G-CSF, erythropoietin, etc) within 2 weeks prior to treatment initiation.	
^b Creatinine clearance should be calculated per institutional standard.	

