5.1.2 Exclusion Criteria

The subject must be excluded from participating in the trial if the subject:

1. Has not recovered (e.g., Grade ≤ 1 or at baseline) from AEs, with the exception of alopecia or Grade ≤ 2 neuropathy, due to a previously administered agent.
 2. Has a diagnosis of immunodeficiency.
 3. Has known additional malignancy that is progressing or requires active treatment. Treatment of an additional malignancy with chemotherapy, immunotherapy, biologic or hormonal therapy must have occurred 2 years prior. Concurrent use of hormones for non-cancer-related conditions (e.g., insulin for diabetes and hormone replacement therapy) is acceptable.
 - a. Note: Local treatment of isolated lesions for palliative intent (e.g., by local surgery or radiotherapy), basal cell carcinoma of the skin, or squamous cell carcinoma of the skin, or ductal carcinoma in situ of the breast that has/have been surgically cured is acceptable.
 4. Has known active CNS metastases and/or carcinomatous meningitis. Subjects with previously treated brain metastases may participate provided the metastases are stable (without evidence of progression by imaging for at least 4 weeks prior to the first dose of study treatment and any neurologic symptoms have returned to baseline), have no evidence of new or enlarging brain metastases, and are not using steroids for at least 7 days prior to the first dose of study treatment.
-

5. Has concurrent unstable or uncontrolled medical condition (e.g. active uncontrolled systemic infection, poorly controlled hypertension or history of poor compliance with an anti-hypertensive regimen, unstable angina, congestive heart failure, uncontrolled diabetes) or other chronic disease, which in the opinion of the investigator, could compromise the patient or the study.
 6. Has an active autoimmune disease requiring systemic treatment within the past 3 months or a documented history of clinically severe autoimmune disease, or a syndrome that requires systemic steroids or immunosuppressive agents.
 - a. Subjects with vitiligo or resolved childhood asthma/atopy would be an exception to this rule.
 - b. Subjects that require intermittent use of inhaled steroids, bronchodilators or local steroid injections may be allowed with sponsor approval.
 - c. Subjects with hypothyroidism stable on hormone replacement or Sjorgen's Syndrome will not be excluded from the study.

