5.2.1.2 Treatment Modification/Delay Due to Adverse Events

The most likely AEs associated with ADXS11-001 are comprised primarily of individual flu-like symptoms (e.g., fatigue, lethargy and low grade fever) or cytokine release symptoms (e.g., constitutional symptoms such as fever, chills, rigors, headache, nausea, vomiting tachycardia, shortness of breath, hypotension, and rash). These symptoms usually present within 2-4 hours after the completion of infusion and are often mild to moderate and transient in nature or respond quickly to symptomatic treatment. In rare instances they may last up to 24 hours. No cumulative or delayed toxicity has been observed.

Less likely AE's include increase heart rate, low blood pressure, muscle aches, headaches, allergic reaction, changes in blood chemistry, changes in blood counts, and short term changes in liver function.

Rare but serious AEs include high fever, difficulty breathing and hypotension.

██████████ ADXS11-001 has a tropism for the liver. Transient asymptomatic elevations of ALT and alkaline phosphatase were observed after dosing in the Phase 1 trial without prophylactic medication administration. For that reason, patients with significant liver disease are excluded, and particular attention is to be paid to hepatic abnormalities. Treatment may be delayed or discontinued for drug related severe and life-threatening toxicities, as shown below in [Table 5](#).

Table 5 Treatment Delay/Discontinuation Guidelines for Drug-Related Adverse Events

Toxicity	Grade	Hold treatment	Timing for restarting treatment	Discontinue subject
Hematologic	1,2,3	No	N/A	N/A
	4	Yes	Toxicity resolves to \leq Grade 1 or baseline	Toxicity does not resolve to \leq Grade 1 or baseline within 3 weeks
	1	No	N/A	N/A
	2-3	Yes	Toxicity resolves to \leq Grade 1 or baseline	Toxicity not resolved to \leq Grade 1 or baseline within 3 weeks of last infusion ^a

[figure not shown]
Non-hematologic, excluding cytokine release symptoms and DLTs	4	N/A	Permanent discontinuation	Permanent Discontinuation from Study
---	---	-----	---------------------------	--------------------------------------

^a With investigator and sponsor agreement, subjects with a non-heme AE (eg alopecia, neuropathy) still at grade 2 after 3 weeks, may continue treatment if only asymptomatic and controlled

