7.2 Assessing and Recording Adverse Events

An AE is defined as any untoward medical occurrence in a patient or clinical investigation subject administered a pharmaceutical product and which does not necessarily have to have a causal relationship with this treatment. An AE can therefore be any unfavorable and unintended sign (including an abnormal laboratory finding, for example), symptom, or disease temporally associated with the use of a medicinal product or protocol-specified procedure, whether or not considered related to the medicinal product or protocol-specified procedure. Any worsening (i.e., any clinically significant

adverse change in frequency and/or intensity) of a preexisting condition that is temporally associated with the use of the Sponsor's product, is also an AE.

Changes resulting from normal growth and development that do not vary significantly in frequency or severity from expected levels are not to be considered AEs. Examples of this may include, but are not limited to, onset of menses or menopause occurring at a physiologically appropriate time.

The Sponsor's product includes any pharmaceutical product, biological product, device, diagnostic agent or protocol-specified procedure, whether investigational (including placebo or active comparator medication) or marketed, manufactured by, licensed by, provided by or distributed by Advaxis for human use.

AEs may occur during the course of the use of Advaxis' product in clinical trials or within the follow-up period specified by the protocol, or prescribed in clinical practice, from overdose (whether accidental or intentional), from abuse and from withdrawal.

AEs may also occur in screened subjects during any pre-allocation baseline period as a result of a protocol-specified intervention, including washout or discontinuation of usual therapy, diet, placebo treatment or a procedure.

All AEs will be recorded from the time the consent form is signed through 30 days following cessation of treatment on the Adverse Event CRF forms/worksheets. The reporting timeframe for AEs meeting any serious criteria is described in [Section 7.2.3.1](#).

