7.2.4 Evaluating Adverse Events

An investigator who is a qualified physician will evaluate all AEs according to the NCI CTCAE v 4.0. Any AE that changes CTCAE grade over the course of a given episode will have each change of grade recorded on the AE CRF/worksheets.

All AEs regardless of CTCAE grade must also be evaluated for seriousness.

The following attribution categories ([Table 12](#)) will be used in assessing the relationship between the AE and the study treatment:

Table 12 Attribution Categories

RELATIONSHIP	ATTRIBUTION	DESCRIPTION
Unrelated to investigational agent/intervention	Unrelated	The AE is clearly NOT related to the intervention
	Unlikely	The AE is doubtfully related to the intervention
Related to investigational agent/intervention	Possible	The AE may be related to the intervention
	Probable	The AE is likely related to the intervention
	Definite	The AE is clearly related to the intervention

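### Section 8.5 gives worsened pre-Day 1 adverse events a shorter or undefined window than new ones, so some late worsening can be collected but not tabulated (minor)

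*Combined protocol and SAP*

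**What the plan says.** Section 8.5 (Analysis of Safety Data) summarizes an AE by either of two routes.

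- New onset: "if the onset date occurs anytime during study treatment or up to 30 days after the last dose of study treatment".
- Onset before Day 1: "or, if it occurs prior to Day 1 and worsens while on therapy".

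The two windows stand side by side in one sentence: "up to 30 days after the last dose of study treatment; or, if it occurs prior to Day 1 and worsens while on therapy". The second route names no period after the last dose, and the text supplied does not define what being on therapy means.

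Collection is not split in this way. Section 7.2 states: "All AEs will be recorded from the time the consent form is signed through 30 days following cessation of treatment". Footnote 9 of the Schedule of Events (Section 6.1) gives 30 days after the last infusion for AEs and SAEs. Section 7.1.2.1 puts new and worsening serious events in a single 30-day window.

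Two further provisions bear on how a worsened event is dated. Section 7.2 makes a clinically significant worsening of a preexisting condition, temporally associated with the product, an AE in its own right. Section 7.2.4 says: "Any AE that changes CTCAE grade over the course of a given episode will have each change of grade recorded". Neither states which onset date a worsened event carries.

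**The concern.** Two events of the same grade, on the same day after the last infusion, can be treated differently in the AE tables only because one of them began before Day 1. The data for both are in the database.

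This matters because safety and tolerability is a secondary objective, the trial has no control arm, and many subjects may enter with existing abnormalities. Exclusion criterion 1 requires recovery from earlier treatment toxicity to Grade 1 or baseline, "with the exception of alopecia or Grade ≤ 2 neuropathy, due to a previously administered agent". Table 3 allows AST and ALT "≤5.0 X ULN for subjects with liver metastases". Section 5.2.1.2 describes a tropism of the product for the liver and says "particular attention is to be paid to hepatic abnormalities". If late worsening is left out of the tables, reported incidence and worst grade can only move down.

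**Working it through.** The plan states no figure to reproduce. The check is of wording, plus the length of the window left uncovered.

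**Step 1. Apply the two routes to three events, each reaching Grade 3 on day 25 after the last dose.**

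- *A new AE with onset on day 25.* Day 25 is within 30 days, so the first route is met and the event is tabulated.
- *An AE that began between consent and Day 1 and first worsens on day 25.* Its onset precedes Day 1, so on its recorded onset it fails the first route. It meets the second only if day 25 still counts as on therapy. Section 7.2.4 records the grade change inside the existing episode and calls for no new onset date. Literally, the event is collected but not tabulated.
- *A condition present before consent that worsens on day 25.* AE recording starts at consent, so the condition is likely to sit in medical history (Section 7.1.1.4). Under Section 7.2 its product-associated worsening is an AE. If onset is dated at the worsening, the first route is met. If the original onset is kept, the outcome is the same as for the second event. The documents do not choose.

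The structure of the rule gives a hint about dating. If every worsening took a new onset date, the first route would already cover worsening during treatment and the second would be redundant. That suggests its authors had original onset dates in mind, but this is inference and not stated text.

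**Step 2. Length of the uncovered window.** Let *d* be the number of days after the final infusion that still count as on therapy. The gap is 30 − *d* days.

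- Therapy ends at the last infusion: *d* = 0, gap = 30 − 0 = 30 days.
- Therapy runs through the 21-day dosing interval (assumption; dosing is every 3 weeks, Section 5.2.5): gap = 30 − 21 = 9 days.
- Therapy includes the whole 30-day follow-up (assumption): gap = 30 − 30 = 0 days.

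The range is 0 to 30 days. The zero-gap reading is the least natural, because the same sentence in Section 8.5 distinguishes the treatment period from the 30 days after the last dose. It is not excluded, however.

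**Step 3. Number of subjects.** This would require the frequency of AEs and conditions present before Day 1 and the rate at which they first worsen after the last dose. The documents give neither, so no count or percentage can be derived.

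**The case against.** The best reply is that most entry abnormalities are already covered. Residual toxicity, neuropathy and raised transaminases normally pre-date consent. Section 7.2 makes their worsening an AE, and dating it at the worsening brings it under the first route with its full 30 days. This stands as a possible reading. It does not settle the matter, because no section fixes the onset date and sites could date identical events differently. It also does not help an AE that begins between consent and Day 1.

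Other points stand in part. Section 8.5 presents clinically significant laboratory abnormalities and Grade 3 or 4 laboratory changes from baseline separately from the AE rule, which answers much of the hepatic worry but not events such as neuropathy. Data listings support the tables and SAEs are reported through 30 days, so no data are lost. Section 8.1 defers analysis details to a SAP, although the text supplied contains no definition that resolves this. The commonest reactions occur 2–4 hours after infusion and usually resolve within 24 hours, and Section 5.2.1.2 reports no delayed toxicity so far. Late worsening is therefore probably uncommon, though not ruled out.

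A reader might infer that baseline toxicities worsening after the final infusion generally vanish from the tables, and that the loss is large. For a subject stopping after one cycle (infusions on Days 1, 22 and 43), follow-up ends on Day 43 + 30 = 73, and 30/73 = 41% of that time could be uncovered. The documents do not support reading this as lost events:

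- It is a share of calendar time, and it assumes that therapy ends at the last infusion.
- Stopping after one cycle is not shown to be typical. With 6-month PFS at the 20% Stage 1 boundary and an exponential curve (assumption), median PFS is 6 × ln 2 / ln 5 = 2.58 months. The proportion progression-free at Day 63 is 0.20^(63/182.4) = 57%, taking 6 months as 6 × 30.4 = 182.4 days. A majority would thus still be progression-free when the second cycle is due.
- Section 5.10 also allows treatment to continue after first radiologic progression.

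**Conclusion.** The point holds as a minor defect in the tabulation rule. Section 8.5 uses two windows where collection uses one. On its literal wording it omits an AE that starts between consent and Day 1 and first worsens after therapy ends but within 30 days of the last dose. Worsening of conditions that pre-date consent may be omitted too, depending on an onset-dating rule that the documents do not give.

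The uncovered period is 0 to 30 days, set by an undefined term. The number of subjects affected is unknown. Any bias in AE incidence or severity is downward. That it is likely small is a judgement, based on the narrow group that certainly fails both routes, the early timing of most reactions and the separate laboratory output. The response and PFS analyses, the Stage 2 decision and the sample size do not depend on this clause.

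**What to change.** In Section 8.5, and in any separate SAP that carries the rule forward:

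- Summarize an AE if it starts, or worsens in CTCAE grade, from the first dose through 30 days after the last dose of study treatment.
- Tabulate the worst grade reached in that window.
- For this purpose, date the onset of a worsened pre-Day 1 event or condition at the worsening. The original onset date can stay in the listings.

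The cost is two or three sentences. No new data are needed, since collection already runs for 30 days after treatment. Reported AE rates may become slightly less favourable.
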